16.1. Training of Clinical Staff

Training of the Investigational Center staff on the conduct of the study and system being studied will be initiated prior to enrollment of the first study subject. All participating physicians and coordinators will be familiarized with the system being studied. Other members of the Investigational Center staff may require training depending on their role listing in the Delegation of Authority Log. Training may contain both lecture and hands-on experience.

The PI is responsible for ensuring that investigational center staff are trained to perform their assigned duties per Delegation of Authority Log. Individual Investigational Center staff must be appropriately trained prior to performing study related tasks.

16.2. Monitoring

Monitoring visits will be conducted at the start, during and at the closure of the clinical study in accordance with Medtronic Standard Operating Procedure (SOP)s and the Monitoring Plan. At minimum, it will be verified whether signed and dated ICFs have been obtained from each subject at the point of enrollment and that AEs discussed in Section 11 were reported via completion of the Adverse Event eCRFs. More details regarding the monitoring activities (frequency of monitoring visits, planned extent of source data verification) are described in the Monitoring Plan.

16.2.1. Accessibility of Investigational Center Staff and Study Materials

The PI(s), his/her delegate(s) and the study coordinator(s) shall be accessible to Medtronic field personnel and the Clinical Study Manager. This accessibility is of particular importance for reviewing data in the eCRF. Direct access to patient medical files for source data verification will need to be granted and prepared prior to any monitoring visits.

16.2.2. Audits and Investigational Center Inspections

In addition to regular monitoring visits, Medtronic may conduct audits at participating investigational centers. The purpose of an audit is to verify the adequate performance of the clinical study related activities. Independent of the employees involved in the clinical study. Regulatory bodies may also perform inspections at participating investigational centers. Any regulatory authority inspection announcements shall be forwarded immediately to the Clinical Study Manager.

The investigator and/or institution shall permit Medtronic and regulatory bodies direct access to source data and documents, taking into account any restrictions due to local law, to perform clinical study-related monitoring, audits, EC review, and regulatory inspections.

16.2.3. Investigational Center Disqualification

Medtronic and/or the EC retain the right to disqualify an investigational center and remove all study materials at any time. Specific instances, which may precipitate investigational center disqualification, include but are not limited to:

- Unsatisfactory subject enrollment with regard to quality and quantity.
- Deviations from CIP, without prior notification and approval from Medtronic.
- Inaccurate, incomplete, and/or untimely data recording on a recurrent basis.

- The incidence and/or severity of adverse experiences in this or other studies indicating a potential health hazard caused by the device.
- Unsatisfactory accountability of study devices.

A written statement fully documenting the reasons for such a termination will be provided to Medtronic, the EC and other regulatory authorities, as required.

16.3. Data Management

16.3.1. Data collection

16.3.2. Electronic Case Report Forms (eCRFs)

The investigator must ensure accuracy, completeness and timeliness of the data reported in the eCRFs and in all other required reports. Data reported on the eCRFs which are derived from source documents must be consistent with the source documents and discrepancies need to be justified in a documented rationale, signed and dated by the (principal) investigator, and filed in the patient medical file.

Only authorized persons can complete eCRFs. eCRFs shall be signed by Investigational Center staff as specified on the Delegation of Authority Log included in the Investigator Site Binder. The OC-RDC system maintains an audit trail on entries, changes or corrections in eCRFs.

A copy of the eCRFs to be used in this clinical study is available under a separate cover, upon request to the sponsor and in the Investigator Site Binder.

Investigational Center will be trained for use of the eCRF prior, or at latest during, Investigational Center initiation visit, on a training database. Access to final eCRFs for study conduct will be granted after training is performed and prior to patient's enrollment.

16.3.3. CareLink iPro

During the course of the study, subject's SG values will be collected and assessed from the iPro2. The iPro2 data needs to be downloaded in CareLink iPro desktop database by the investigator or designated Investigational Center staff. The Study Meter data from the Patient Log Sheet needs to be obtained by the investigator or designated Investigational Center staff and entered into CareLink iPro.

The data in the different databases are linked to each other via the SIDs, which is a 9-digit code (313XXXXXX) to prevent subject identification by the sponsor.

16.3.4. Patient Log Sheet & Subject Questionnaires

The Patient Log Sheet and subject questionnaires will be collected on paper that will be kept at the Investigational Center. The investigator, or designated Investigational Center staff, will then copy the data from the Patient Log Sheet and answers of the subject on the paper questionnaires into OC-RDC

system. It is important that the investigator or designated Investigational Center staff verifies questionnaires for completeness.

16.3.5. Time windows for completion and submission of eCRFs

It is expected that eCRFs are completed in a timely manner with the exception of reportable AEs (see Section 11.3), which need to be recorded within 24 hours in the eCRF after awareness of the investigator or Investigational Center staff to the event. Most eCRFs should be submitted in final form, i.e. saved as complete, upon data entry, so that Monitors can proceed with data verification without delay. Exceptions to this rule may apply to eCRF that need to be accessed on multiple occasions before they can be finalized (e.g. Device Accountability eCRF).

16.3.6. Data review and processing

The leading investigational center will be accountable for data management and analysis about the data from each clinical research institution in a centralized manner according to local regulations and study requirements. Medtronic will oversee all data management functions and provide support if necessary. Collected data will be reviewed for completeness, correctness and consistency, as per the monitoring plan. In case of issues, queries will be entered on the respective eCRF for the investigator to complete, correct or comment on the data.

16.4. Direct Access to Source Data/Documents

The patient's hospital/clinic file, CareLink iPro data, laboratory reports, and data collected on the Patient Log Sheets and questionnaires are handled as source data.

In addition, Investigational Centers will receive visit requirement instructions that detail required activities and data to be collected during the patient visits. The objective of these instructions is to remind the Investigational Center of all study-related procedures to be performed and items to be recorded, before data is actually entered into the study database.

Medtronic clinical representatives or delegates, will be granted access by the Investigational Center to all source documents including electronic source documents, if applicable, purposes of monitoring, audit or inspection. Where copies of the original source document as well as printouts of original electronic source documents are retained, these shall be signed and dated by a member of the Investigational Center team with a statement that it is a true and complete reproduction of the original source document.

16.4.1. Quality Audits

Medtronic reserves the right to conduct quality audits at the investigational center in order to verify adherence to external regulations and internal policies and procedures; assess adequacy and effectiveness of clinical policies and procedures; assure compliance with critical study requirements;

confirm integrity and accuracy of clinical study data; and protect the safety, rights and welfare of study subjects.

16.5. Confidentiality

All records and other information about subjects participating in this clinical study will be treated as confidential.

Subject confidentiality will be maintained throughout the clinical study to the extent permitted by law. That is, every attempt will be made to remove subject identifiers from clinical study documents. For this purpose, a unique SID code (study - investigational center - subject number) will be assigned and used to allow identification of all data reported for each subject.

This will also ensure that the information can be tracked back to the source data.

Study data may be made available to third parties, e.g., in the case of an audit or inspection performed by regulatory authorities, provided the data are treated confidentially and that the subject's privacy is guaranteed. The identity of a subject will never be disclosed in the event that study data are published. Only anonymized data will be analyzed and published.

16.6. Liability

Medtronic maintains appropriate clinical study liability insurance coverage as required under applicable laws and regulations and will comply with applicable local law and custom concerning specific insurance coverage. If required, a clinical study insurance statement/certificate will be provided to the EC.

If the investigational devices have caused any damage to the testing subjects, the sponsor will compensate in accordance with the contract of clinical trials.

Finance information will be documented in Clinical Trial Agreement.

16.7. Probability analysis of success

Since the Enlite Sensor has been evaluated in previous clinical studies and has demonstrated a within 20% agreement rate, significantly higher than 60% the probability that the acceptance criteria of 60% will be met within this study is extremely rather high.

16.8. Probability analysis of failure

Since the Enlite Sensor has been evaluated in previous clinical studies and has demonstrated a within 20% agreement rate, significantly higher than 60% the probability of failure is extremely low.

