14.5. Sample Size and Power

The sample size selected is based on the primary analysis of the primary effectiveness endpoint (i.e., accuracy), agreement in comparative readings of paired sensor and YSI glucose readings.

Based on previous study, using one sample T test (formula provided below) with a level of 0.975 (one sided), β of 0.8, μ_0 is 0.6, μ_α is 0.72 and σ is 0.32:

$$n = \sigma^2 \frac{(t_\alpha + t_\beta)^2}{(\mu_0 - \mu_\alpha)^2}$$

It is indicated that a sample size of 58 will have power greater than or equal to 80% to demonstrate that the overall agreement rate is greater than 0.6. Considering 20% drop out, we need to enroll 72 subjects.

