14.6. Analysis Populations, handling of missing data, error

Data entry error or non-reasonable values will be cleaned before data analysis. No imputations will be done for missing data. All enrolled subjects who have at least one paired Enlite Sensor and YSI measurement will be included in the efficacy analysis population. All enrolled subjects who have a Enlite Sensor inserted will be included in the safety analysis population.

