14.9. Statistical Model and Analyses of Primary Endpoint

Sensor values from primary sensor will be compared to YSI plasma glucose values during YSI FSTs. A within 20% mean agreement rate (± 20 mg/dL (1.1 mmol/L) when Reference BG less than or equal to (\leq) 80 mg/dL (4.4 mmol/L) between Enlite Sensor values and YSI plasma glucose values during YSI FST days defined as μ will be evaluated against the null Hypothesis:

$$H_0: \mu \leq 60\%$$

$$H_1: \mu > 60\%$$

- Statistical testing

One sample T test will be used for the analysis of the primary endpoint. The 97.5% lower confidence limit of the mean agreement rate will be tested against corresponding threshold.

- Missing data
No imputation for missing data will be performed.
- Pass/Fail Criteria
The study pass/fail criteria is based on statistical hypothesis of the primary endpoint. If the 97.5% lower confidence limit is greater than 60%, the study will be considered as success.
- Justification for Exclusion of Particular Information from the testing of the Hypothesis
Not Applicable

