6.2 Sample Size Determination

The sample size selected is based on the primary effectiveness endpoint (i.e., accuracy), agreement in comparative readings of paired sensor and YSI glucose readings.

Based on pervious study, using one sample T test (formula provided below) with α level of 0.975 (one sided), β of 0.8, μ_0 is 0.6, μ_α is 0.72 and σ is 0.32:

$$n = \sigma^2 \frac{(t_\alpha + t_\beta)^2}{(\mu_0 - \mu_\alpha)^2}$$

it is indicated that a sample size of 58 will have power greater than or equal to 80% to demonstrate that the overall agreement rate is greater than 0.6. Considering 20% drop out, we need to enroll 72 subjects.

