6.9 Significance Level and Statistical Analysis Software

For the statistical analysis of the primary endpoint and secondary endpoints, the level of significance will be set at one-sided 0.025. The level of significance of tests performed on other indicators will be set at two-sided 0.05 level (except special cases). SAS® 9.4 statistical software and R3.5.2 are applied for statistical analysis.

7. Indicators and Statistical Analysis Methods

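### Does the protocol's claim that failure is very unlikely contradict its own 80% power calculation?

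*Protocol*

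**What the plan says.** Protocol 14.9 sets the pass/fail rule: "If the 97.5% lower confidence limit is greater than 60%, the study will be considered as success". The test is a one-sample t test on the mean within-20% agreement rate.

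Protocol 14.5 powers that test against a null of 0.60, with an assumed mean of 0.72 and an SD of 0.32 taken from an unnamed previous study. It concludes that "a sample size of 58 will have power greater than or equal to 80" percent, and adds a 20% dropout allowance to reach 72 enrolled. SAP 6.2 repeats the calculation.

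In the Study Administration chapter, Protocol 16.7 says that "the probability that the acceptance criteria of 60% will be met within this study is extremely rather high", and 16.8 says that "the probability of failure is extremely low". Both sections give one reason: earlier clinical studies of the sensor showed agreement significantly above 60%. Neither gives a rate, an SD, a sample size or a calculation.

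**The concern.** The event described in 16.7 and 16.8 is the event powered in 14.5. Power is the probability of meeting the criterion if the planning values are true, and its complement is the probability of failing. A design with 80% power at its planning values fails about one time in five at those values, which nobody would call extremely low.

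A reader who compares the two places gets two different pictures of the same trial. The sections are titled as probability analyses but contain no analysis. An earlier result above 60% does not by itself make it nearly certain that the lower limit in a new study of about 60 subjects will clear 60%. If an ethics committee or investigator relied on section 16 alone, they could come away overconfident about the trial's prospects.

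**Working it through.** **Inputs**

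- Null 0.60, assumed mean 0.72, SD 0.32: Protocol 14.5, SAP 6.2.
- One-sided significance level 0.025. Protocol 14.5 writes it as a confidence level, "with a level of 0.975 (one sided"). SAP 6.9 confirms that "the level of significance will be set at one-sided 0.025".
- Evaluable number: 58 from 14.5, about 60 expected completers from Protocol section 6, and 72 as the enrolment cap.

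**Step 1: reproduce the plan's figure.** The protocol's formula is n = SD² × (t_α + t_β)² / (difference)². With 57 degrees of freedom, t_α = 2.002 and t_β = 0.848:

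n = (0.32/0.12)² × (2.002 + 0.848)² = 7.111 × 8.12 ≈ 57.8, which rounds up to 58.

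Exact power from the noncentral t distribution (n − 1 degrees of freedom, noncentrality (0.12/0.32) × √n) is 79.5% at n = 57 and 80.2% at n = 58. The stated 58 is the smallest number that reaches 80%, so 14.5 is right.

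**Step 2: probability of failure at the planning values.** Failure is the probability that the t statistic falls below its critical value.

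| Evaluable n | Noncentrality 0.375 × √n | Critical t | Failure |
|---|---|---|---|
| 58 | 2.856 | 2.002 | 19.8% |
| 60 | 2.905 | 2.001 | 18.5% |
| 66 | 3.046 | 1.997 | 14.9% |
| 72 | 3.182 | 1.994 | 11.9% |

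The n = 72 row is a best case, because 72 is the cap before dropout and Protocol 8.2 counts enrolment from consent. The evaluable number can still exceed the number of completers, because Protocol 14.6 asks for only one sensor–YSI pair: "All enrolled subjects who have at least one paired Enlite Sensor and YSI measurement will be included in the efficacy analysis population".

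**Step 3: what would make the wording true?** The values below are assumptions, not figures from the documents. All use n = 58.

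| True mean | SD | Failure |
|---|---|---|
| 0.72 | 0.32 | 19.8% |
| 0.75 | 0.32 | 6.1% |
| 0.754 | 0.32 | 5.0% |
| 0.783 | 0.32 | 1.0% |
| 0.72 | 0.249 | 5.0% |
| 0.72 | 0.210 | 1.0% |

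Raising the true mean by about 0.03 cuts the failure risk from 20% to 6%. Raising it by about 0.06 brings it to 1%. The answer depends heavily on the prior data, which the documents do not report.

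**Step 4: does anything use the two sentences?** The sample size comes from 14.5, the test and decision rule from 14.9, the analysis sets from 14.6 and SAP 6.3, and the stopping rules from 9.14. None of these refers to 16.7 or 16.8.

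**The case for a change.** The strongest case for a change is that both statements are current protocol text about the one criterion that decides the study, and only one of them is backed by numbers. Neither document calls 0.72 and 0.32 conservative. Section 14.5 says they come from a previous study, which is the same kind of evidence that 16.7 and 16.8 invoke. If that study is the sponsor's best guide to the truth, near-certainty does not follow. Amending two sentences, or citing the prior mean and SD, would cost very little.

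Most of this stands as a description. The wording is unsupported, and the phrase used in 16.7 is garbled. What does not follow is a proven contradiction. Power in 14.5 is conditional on one chosen alternative, while 16.7 and 16.8 state an expectation about the actual result. A sponsor may size a trial on a modest alternative and still expect to do better. The two conflict only if 0.72 and 0.32 are the best estimates, and the documents do not say that either. Section 14.5 refers to a single study and 16.7 and 16.8 to several. The grammar is too loose to rest much on, but the evidence behind the two may differ and cannot be seen here.

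**Conclusion.** No change to the plan is called for. Under the documents' only planning values, the chance of missing the 60% criterion is about 18–20% with 58 to 60 evaluable subjects, and about 12% if all 72 were evaluable. These figures assume that 0.72 and 0.32 are the true values and that subject-level rates are close enough to normal for the t test. On that footing the language of 16.7 and 16.8 is too strong for what the protocol shows.

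It is nevertheless loose qualitative wording in an administrative chapter. No stated number is wrong, and a reader who wants the design's operating characteristics finds them correctly given in 14.5 and SAP 6.2. Rewording the sentences would alter nothing the trial does or can conclude. If the protocol is reopened for other reasons, the sponsor could cite the prior-study figures or soften the language as an editorial courtesy.

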16.9. Responsibilities of all parties

Investigator responsibilities will be included in clinical trial agreement and subject responsibilities will be available in Informed Consent Form (ICF). Sponsor will undertake all the responsibilities of the sponsor as required per CFDA regulations.

16.10. CIP Amendments

An investigator or study team member can propose any appropriate modification(s) of the CIP or study device/product or study device/product use. Medtronic will review this proposal and decide whether the modification(s) will be implemented.

Medtronic can decide to review the CIP based on new information (i.e. from an investigator, the CEC or the study team) and will submit any significant amendment to the CIP, including a justification for this amendment, to the appropriate regulatory agency (if applicable) and to the investigators to obtain approval from their EC. The investigator will only implement the amendment after approval of the EC, regulatory agency (if applicable) and sponsor. Administrative amendments to the CIP will be submitted to the EC for notification. Furthermore investigators shall sign any approved amendment for agreement.

16.11. Records and reports

16.11.1. Investigator Records

At a minimum, the following records must be kept by the investigator:

- All essential study documents and correspondence that pertains to the clinical study
- CIP and, if applicable, any amendments
- Investigator's Brochure and/or user guide
- Medtronic and EC-approved Patient ICF
- EC and Regulatory authority approval or notification
- Fully signed clinical study agreements (i.e. including Investigator Statement and Signature Page, Clinical Trial Agreement and Confidential Disclosure Agreement)
- Completed Delegation of Authority Log
- Training documentation of all investigational center staff
- Subject screening log and/or SID log
- Signed, dated and fully executed Patient ICFs
- Source document requirements
- Fully executed eCRFs and corrections
- Report of AEs and Device Deficiencies
- Device accountability records
- CIP Deviation/ CIP Non Compliance, if any
- Clinical Bulletins- A brief official update or summary of current study news on a matter of immediate interest and high importance to investigational center surrounding the CIP.

- Current signed and dated curriculum vitae (CV) of PI (and key study team members if required per local requirements)
- Study reports

16.11.2. Investigator reporting responsibilities

Table 4. Investigator Reporting Requirements

Report	Submit to	Description/Constraints
Study deviations	Management department of medical device clinical study then they will submit to Sponsor and EC	Any deviation from the clinical investigational plan shall be recorded together with the explanation of the deviation. Protocol deviation that may affect the subjects' rights and interests, safety, health or the scientificity of clinical trials, including deviation regarding requests and reports
Failure to obtain informed consent	Sponsor and EC	Informed consent shall be obtained in writing and documented before a subject is enrolled into the clinical investigation. (ISO 14155:2011)
Progress report	Management department of medical device clinical study then they will submit to Sponsor and EC	During the clinical trials, the investigators should notify sponsor and report to the EC in a timely manner by promptly reporting the progress report to the medical device clinical trial administration department of the investigational centers, including the safety summary and deviation report.
Final report	
 • Management department of medical device clinical study then they will submit to Sponsor and EC (if needed per EC requirements) • CFDA 	
Upon completion of multi-center clinical trials, investigators of all investigational centers shall issue brief summary of clinical trials, respectively, and submit it to coordinating investigator together with eCRFs upon review as required for coordinating investigator to summarize and complete summary report.
 
(CFDA order No.25 Article 29 (7))
 
Investigators should, in accordance with the design requirements of the clinical trial protocol, verify and validate the safety and effectiveness of investigational medical devices, and complete the Clinical Trial Report. As for multi-center clinical trials, the Clinical Trial Report should contain the Summaries of Clinical Trial of all sub-centers.

Report	Submit to	Description/Constraints
		
(CFDA order No.25 Article 83)
 
The Clinical Trial Report should be signed and dated by the investigators, and submitted to the sponsor after being reviewed, commented, dated and sealed by medical device clinical trial administration department of clinical trials institutions.
 
For multi-center clinical trial, the clinical trial summary of each center should be signed and dated by the investigators of respective center, and submitted to the leading investigational center after being reviewed, dated and sealed by the investigational center's clinical trial administration department.
 
(CFDA order No.25 Article 86)

Other	EC and CFDA	
An investigator shall, upon request by a reviewing EC, CFDA or any other regulatory agency, provide accurate, complete, and current information about any aspect of the investigation.

